#### **6.3.3.2. Historical Illness and Prior Therapies**

Historical illnesses are clinically relevant events in the past that ended before the pre-study visit. Historical illnesses will be coded according to the most current version of the Medical Dictionary for Regulatory Activities (MedDRA) dictionary and listed for all patients on therapy by cohort and study phase.

Pre-existing conditions are existing clinically relevant events that started prior to the study. The conditions will be graded using the CTCAE CCI and it will be presented in the AE listings.

Prior therapies are procedures completed before the pre-study visit and include any therapy administered prior to the first dose of the study drug. The therapies, including radiotherapy, surgery, systemic and topical, will be listed for each study phase and summarized for patients on therapy by cohort and overall in each study phase.

Post-treatment therapies will be listed for all patients on therapy.

#### **6.3.3.3. Concomitant Medication**

All medications will be coded to the generic preferred name according to the current World Health Organization (WHO) drug dictionary.

All concomitant medications will be listed and summarized using the preferred name for all patients on therapy by cohort.

### **6.3.4. Study Drug Exposure**

LY2835219 will be supplied as 25-mg and 150-mg capsules in 28-count bottles for oral administration by Eli Lilly and Company.

Clinical trial (CT) lot numbers will be listed for all patients on therapy.

Study drug data will be listed for all patients on therapy. At least the data on LY2835219 will include dose level assignment, administration date and time, actual dose administered, number of capsules taken and responses to the patient compliance CRF question.

A summary of LY2835219 drug exposure will be presented. Within this table, the maximum number of completed cycles of study drug per patient will be summarized. A completed cycle is any cycle for which the patient was compliant with study drug as defined in Protocol Section 6.6.

A summary of LY2835219 dose administration, detailing the number of doses given as planned, increased, reduced, omitted and cycle delays will be presented by cohort and cycle.

LY2835219 drug intensity will be listed and summarized by cycle and overall for all patients on therapy by cohort.

Drug Intensity (DI) is defined as follows:

$$DI(\%) = \left( \frac{Actual\_cumulative\_dose\_taken}{Planned\_cumulative\_dose} \right) * 100$$

### **6.3.5. Safety Analyses**

#### **6.3.5.1. Dose Limiting Toxicity and Maximum Tolerated Dose Estimation**

Dose limiting toxicities, for Part A cycle 1, and DLT-equivalent toxicity, for all cycles except Part A cycle 1, will be listed and summarized for all patients on therapy by cohort.

To guide dose selection and to find the MTD, a logistic regression model will be fitted to the data to establish the relationship between the dose and the probability of experiencing a DLT. The model-based MTD estimate, defined as the highest dose level at which no more than 33% of patients experience a DLT during cycle 1, will be estimated from the model together with its confidence limits.

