5.2. Summary of Study Design

This study is a multicenter, nonrandomized, open-label, dose-escalation Phase 1 trial of LY2835219 in approximately 300 patients with advanced cancer. During dose escalation (Part A), 33 patients were treated across 2 schedules. For the once daily schedule, patients received LY2835219 orally every 24 hours. For the twice daily schedule, patients received LY2835219 orally every 12 hours for Days 1 through 28 of a 28-day cycle (refer to [Figure JPBA.5.1](#)), with modifications during Cycle 1 to enable PK sampling following a single dose and repeated doses. During dose escalation, cohorts of at least 3 patients were enrolled at each of the planned dose levels.

[figure not shown]
During dose escalation (Part A), 33 patients were treated across 2 schedules. For the once daily schedule, patients were treated at 50, 100, 150, and 225 mg every 24 hours (Q24H). For the twice daily schedule, patients were treated at 75, 100, 150, 200, and 275 mg every 12 hours (Q12H). An MTD for the once daily schedule was not reached, whereas the MTD for the twice daily schedule was tentatively established (pending dose confirmation) at 200 mg Q12H. As depicted in [Figure JPBA.5.1](#), the study design consists of a *dose escalation phase (Part A)* and *6 tumor-specific expansion phases (Parts B, C, D, E, F, and G)*. The dose escalation phase

(Part A), described in Section 6.2.2, was guided by safety assessments from Days 1 through 28 of Cycle 1 for all patients in the cohort and also by the emerging PK data. Dose escalation occurred until the MTD (defined in Section 6.2.2.1) was determined for at least 1 schedule.

After the last patient enrolled in the dose escalation phase (Part A) completes Cycle 1, then the 6 tumor-specific expansion phases (Parts B, C, D, E, F, and G) may begin. In each tumor-specific expansion phase, at least 15 and up to 45-60 patients will be treated on the twice daily schedule at a dose no greater than the MTD (200 mg every 12 hours) with administration of LY2835219 on Days 1 through 28 of a 28-day cycle, with modifications during Cycle 1 to enable PK sampling following a single dose and repeated doses. Patients enrolled in Part G should receive fulvestrant according to the study schedule.

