For dose escalation (Part A), any patient who is discontinued from the study before receiving at least 75% of planned doses of LY2835219 in Cycle 1 will be deemed nonevaluable for assessment of that dose level and may be replaced unless they experience a DLT before withdrawal. Nonevaluable patients may be replaced to ensure that no fewer than 3 patients receive at least 75% of planned doses of LY2835219 in Cycle 1 at each dose level, unless enrollment to that cohort has stopped because more than 1 patient at that dose level has experienced a DLT. Patients who complete Cycle 1 of therapy but are not evaluable for PK may be replaced upon consultation with the investigator(s) and the Lilly CRP to ensure adequate PK

data collection, unless enrollment to that cohort has stopped because more than 1 patient at that dose level has experienced a DLT.

For Part G, any patient who is discontinued from the study for a reason other than progressive disease and before receiving a post-treatment radiological tumor assessment will be deemed nonevaluable for assessment of response. Additional patients may be enrolled to replace nonevaluable patients.

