- d Additional guidance for ILD/pneumonitis monitoring is provided in Section [7.1.3.4](#).

Dose adjustments as outlined in [Table JPBA.6.3](#) are allowed both within a cycle and between cycles. LY2835219 dose alterations (omission, reduction, and discontinuation) should not be based solely on the presentation of serum creatinine values, because these may not reflect actual renal function. Further information can be found in the Section 3.2.4 of the LY2835219 IB.

If a patient who, in the judgment of the investigator, is receiving clinical benefit from study therapy requires further dose reduction than is outlined in [Table JPBA.6.3](#), then the investigator must discuss with the Lilly CRP prior to any further dose reduction.

For patients requiring dose reduction(s), re-escalation to a prior dose level is permitted only after consultation with the Lilly CRP.

Dose omissions are allowed within a cycle. If a patient requires omission of more than 25% of doses during a cycle for tolerability, then treatment may continue if the investigator determines the patient is receiving clinical benefit.

Table JPBA.6.3. Dose Adjustments of LY2835219 for Study I3Y-MC-JPBA

| Dose Adjustment | Oral Dose | Frequency |
|-----------------|-----------|----------------|
| 0 | 200 mg | Every 12 hours |
| 1 | 150 mg | Every 12 hours |
| 2 | 100 mg | Every 12 hours |
| 3 | 75 mg | Every 12 hours |

For patients in Part G with moderate hepatic impairment (defined as Child-Pugh Class B), fulvestrant 250 mg should be administered intramuscularly into the buttock slowly (1 to 2 minutes) as one 250-mg injection, according to the study schedule. In the event that fulvestrant must be discontinued, a patient may continue to receive LY2835219.

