9.1.4. Safety Analyses

Safety analyses will be conducted on all patients who have received at least 1 dose of the study drug.

All patients who receive at least 1 dose of LY2835219 will be evaluated for safety and toxicity. Adverse events will be classified using the CTCAE **CCI**

Safety analyses will include summaries of the following:

- AEs, including severity and possible relationship to study drug
- Dose adjustments
- DLTs
- Laboratory measures and electrocardiograms.

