**Table JPBA 6.1. Data Handling Conventions**

Term	Definition or Rule
Entered	Patients entered into the trial as those who sign the informed consent document directly or through their legally acceptable representatives.
Enrolled	Patients who are enrolled in the trial are those who have been assigned to a treatment.
On therapy	Patients who have received at least one dose of LY2835219.
Phase	This study has 2 phases: Dose Escalation Phase (Part A) and Dose Confirmation Phase (Part B, C, D, E F, and G).
Study day	
 
• There is no study day 0. Day -1 is the day before the day 1 of cycle 1 of each phase.
 
• Day -3 of cycle 1 of Dose Escalation Phase is the first dose of LY2835219.
 

Cycle day	
 
• There is no cycle day 0. Cycle day -1 is the day before the cycle day 1 of cycle 1 of each phase.
 
• Day -3 of cycle 1 is the first dose of LY2835219 in each phase. Day 1 of cycle 2 and beyond is the first dose of LY2835219 within cycle for each phase.
 

Treatment Day	Treatment Day relative to first day of the study (Cycle 1 Day -3).
Baseline	
For change from baseline analyses, baseline value is defined as the last reported measure on or before the first dose date (prior to the dose administration), unless otherwise specified.
 
For change from baseline within a cycle, baseline value is defined as the measure prior to the first dose of that cycle, unless otherwise specified.

The following are the General Reporting Requirements for the non-PK analyses (Table JPBA.6.2).

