## Appendix 2. List of Tables, Listings and Figures

---

Note: some of these outputs may be combined into single tables/listings (for example, all PK parameters) or expanded to several outputs.

14.1	Demographic Data	
14.1-1.1	Summary of Patient Disposition	(all patients)
14.1-2.1	Summary of Patient Demographics	(patients on therapy)
14.1-2.2	Summary of Baseline Disease Characteristics	(patients on therapy)
14.1-2.3	Summary of Historical Illnesses	(patients on therapy)
14.1-2.4	Summary of Reported Prior Therapies	(patients on therapy)
	Study Drug/Compliance	
14.1-3.1	Summary of Study Drug Exposure	(patients on therapy)
14.1-3.2	Summary of Drug Administration	(patients on therapy)
14.1-3.3	Summary Study Drug Intensity – by patient	(patients on therapy)
14.2	PK/PD/Efficacy Data	
14.2-1.1	Summary of Maximum Tolerated Dose Estimation	(patients on therapy)
14.2-1.2	Analysis of Maximum Tolerated Dose Estimation	(patients on therapy)
14.2-2.1	Summary of LY2835219 PK parameters	(PK population)
14.2-2.2	Analysis of LY2835219 PK parameters	(PK population)
14.2-2.3	Analysis of Dose Proportionality	(PK population)
14.2-3.x	Summary of [PD endpoint] Data (Titles to be updated accordingly by endpoint)	(PD population)
14.2-4.1	Summary of Best Overall Response	(efficacy population)
14.2-4.2	Summary of Time to Events	(efficacy population)
14.3.1	Adverse Events	
14.3.1-1.1	Summary of Pre-existing Conditions – Preferred Term by Decreasing Frequency within System Organ Class	(patients on therapy)
14.3.1-1.2	Summary of Adverse Events Preferred Term by Decreasing Frequency within System Organ Class	(patients on therapy)
14.3.1-1.3	Summary of Study Drug Related Adverse Events Preferred Term by Decreasing Frequency within System Organ Class	(patients on therapy)
14.3.1-1.4	Summary of Maximum Laboratory Investigator Determined CTC Adverse Events Grade Post Baseline - Regardless of Study Drug Relatedness	(patients on therapy)
14.3.1-1.5	Summary of Maximum Laboratory Investigator Determined CTC Adverse Events Grade Post Baseline - Possibly Drug Related	(patients on therapy)
14.3.1-1.6	Summary of Dose Limiting Toxicities	(patients on therapy)
14.3.1-1.7	Summary of Maximum Laboratory Investigator Determined CTC Adverse Events Grade Post Baseline - Possibly Drug Related	(patients on therapy)
14.3.1-1.8	Summary of Dose Limiting Toxicities	(patients on therapy)

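### The SAP's MTD outputs use every treated patient, so any Part A patient the protocol deems nonevaluable would count as DLT-free; the model's dose metric and the DLT windows also need settling

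*SAP*

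**What the plan says.** **Model and population.** SAP 6.3.5.1 states that "a logistic regression model will be fitted to the data to establish the relationship between the dose and the probability of experiencing a DLT", and that the model-based MTD will be reported with confidence limits. Appendix 2 lists a summary (14.2-1.1) and 14.2-1.2, "Analysis of Maximum Tolerated Dose Estimation". Both are labelled for patients on therapy, which SAP Table JPBA 6.1 defines as "Patients who have received at least one dose of LY2835219". SAP 6.2 has safety, PK, PD, PK/PD and efficacy sets but none for DLT evaluability. The one exclusion listing (16.2.3-1.1) covers PK, PD and efficacy only.

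**Evaluability rule.** For Part A, Protocol 5.3.1 says "any patient who is discontinued from the study before receiving at least 75% of planned doses of LY2835219 in Cycle 1 will be deemed nonevaluable" and continues "for assessment of that dose level and may be replaced unless they experience a DLT before withdrawal".

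**Neighbouring rules.** Protocol 9.1.4: "All patients who receive at least 1 dose of LY2835219 will be evaluated for safety and toxicity". Protocol 6.2.4.1: "If a patient requires omission of more than 25% of doses during a cycle for tolerability, then treatment may continue", provided the investigator sees clinical benefit.

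**Windows.** The Part A DLT window starts on Day -3 in both documents. It ends on Day 29 in Protocol 6.2.2.1 and on Day 28 in SAP 6.1.1. For Parts B-G, Protocol 6.2.2.1 starts the Cycle 1 DLT-equivalent window on Day 1. SAP 6.1.1 counts such events in Parts B-G whatever the cycle, and SAP 6.3.5.1 counts them in all cycles except Part A Cycle 1. Neither SAP section sets a Day 1 start. The first dose is on Day -3 (Protocol 6.2.1 and Attachment 1, footnote f), and SAP Table JPBA 6.1 places that day inside Cycle 1 of each phase.

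**The concern.** A patient who leaves early without a DLT has not been observed for the whole DLT period. The protocol therefore does not let that patient inform the dose level. A binary DLT model run on everyone with at least one dose would code the same patient as a zero. The bias runs one way: DLT risk down, model-based MTD up. The model-based MTD with its confidence limits is a planned output bearing on the primary objective, safety and tolerability.

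The SAP also does not say which dose enters the model or how the once-daily and twice-daily schedules are combined, and the fitted risk depends on that choice.

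The window mismatch bears on a different decision. Protocol 6.2.3 stops accrual to an expansion for a safety review when DLT-equivalent toxicity reaches 33% or more of its patients. A qualifying event on Days -3 to -1 would count under the SAP and not under the protocol.

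**Working it through.** **1. Reproduce the stated MTD.** Protocol 4.7 gives 1 DLT in 7 patients at 200 mg Q12H and 2 in 3 at 275 mg Q12H. With Clopper-Pearson 95% limits, 1/7 = 14.3% (0.4-57.9%), below 33%, and 2/3 = 66.7% (9.4-99.2%), above it. The MTD of 200 mg Q12H follows.

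**2. The 75% line.** Protocol 6.2.1 gives 1 dose on Day -3 plus 55 later doses in twice-daily Cycle 1. That is 56 doses, and 0.75 x 56 = 42.

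**3. Inputs to the model.** Part A treated 33 patients (Protocol 5.2). Counts at the other seven dose levels are not given. Protocol 5.2 says only that "cohorts of at least 3 patients were enrolled at each of the planned dose levels". I assume no DLT at those levels and three patients in each. That leaves 33 - 7x3 - 7 - 3 = 2 patients, placed in all 7x8/2 = 28 possible ways over those seven cohorts.

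**4. Fit.** The model is logit p(d) = a + b·d, and the dose with 33% risk is D33 = [ln(0.33/0.67) - a]/b. The comparison is 1/7 at 200 mg Q12H against 1/6, that is, with one DLT-free patient assumed nonevaluable. The observed rate moves from 14.3% to 16.7% (0.4-64.1%). Modelled risk at 200 mg Q12H, range over the 28 placements:

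| Specification (linear in dose) | n = 7 | n = 6 | Rise (points) |
|---|---|---|---|
| Twice-daily cohorts only | 11.6-12.2% | 12.9-13.7% | 1.3-1.5 |
| Both schedules, total daily dose | 11.2-11.8% | 12.4-13.1% | 1.2-1.3 |
| Both schedules, mg per administration | 5.8-7.3% | 6.2-7.9% | 0.4-0.6 |

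D33 moves from 234.3-234.9 to 232.0-232.8 mg Q12H (twice-daily cohorts), or from 469.1-470.1 to 464.8-466.1 mg/day (total daily dose). Modelled risk at 275 mg Q12H is 59-71% over all these fits. So 200 mg Q12H stays below 33% and 275 mg Q12H above it. The Wald 95% limits at 200 mg Q12H (twice-daily, n = 7) run from 1.8-1.9% to 47.7-49.9%.

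**5. Sensitivity.** With log dose in the twice-daily fit, the risk is 12.6-13.1% for n = 7 and 14.1-14.9% for n = 6, a rise of about 1.5 to 1.8 points. With one, two or three patients removed (linear, twice-daily, three patients at each lower level), the risk goes from 12.2% to 13.7%, 15.5% and 17.7%. The observed rates are then 1/6 = 16.7%, 1/5 = 20.0% and 1/4 = 25.0%. Only 1/3 = 33.3% would fail the observed-rate rule, and that needs four of the seven to be nonevaluable.

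**6. Why mg per administration departs.** It ranks 225 mg Q24H (225 mg/day) above 200 mg Q12H (400 mg/day). The assumed DLT-free patients at 225 mg then pull the curve down at 200 mg.

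**7. Pause review.** The smallest counts reaching 33% are ceil(0.33 x 15) = 5, ceil(0.33 x 45) = 15 and ceil(0.33 x 60) = 20, each 33.3%. One patient fewer gives 4/15 = 26.7%, 14/45 = 31.1% and 19/60 = 31.7%. One event on Days -3 to -1 can therefore decide whether the review is triggered.

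**The case against.** The best reply is that the Appendix 2 label is generic. Patients on therapy spans Parts A to G, whereas SAP 6.1.1 and 6.3.5.1 already tie DLTs and the MTD to Part A Cycle 1, so the label cannot be the literal model set. The SAP writes no coding rule for an incomplete Cycle 1. Shells and data set specifications are separate documents, and part of SAP 6.3.1 is redacted. This stands as a caution: counting as a non-event is what the label implies, not something the SAP says. It does not remove the gap, because no visible text carries the protocol's rule into the two outputs.

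A second reply is that Protocol 9.1.4 evaluates every treated patient for toxicity. That is right for DLT listings and summaries, but it does not settle the denominator of a dose-level estimate that Protocol 5.3.1 governs.

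Several stronger readings are tempting, and the documents do not support them:

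- *Nonevaluable patients were in fact counted.* Seven patients at 200 mg Q12H against up to six in Protocol 6.2.2 may suggest a replacement. Protocol 5.3.1 also allows replacement for PK reasons, so the count proves nothing.
- *Everyone below 75% of doses should be excluded.* The rule requires discontinuation from the study. Patients who omit doses and continue are outside it.
- *Days -3 to -1 are covered nowhere in Parts B-G.* The SAP's wording covers them; only the protocol starts at Day 1.
- *The two MTD inequalities matter.* SAP 6.3.5.1 allows a rate equal to 33%, whereas SAP 6.1.1 and Protocol 6.2.2.1 require a rate below it. Since 0.33 = 33/100 in lowest terms, no observed rate with n up to 60 equals it, and 1/3 fails both. The difference is editorial.

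The Day 28 and Day 29 endings may be version lag. The SAP rests on amendments (f) and (g), the supplied protocol is amendment (j), and the intermediate text is not available.

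**Conclusion.** The point holds and is minor. As labelled, the MTD outputs do not respect the protocol's evaluability rule, and the direction of any bias is known. Its size is conditional on a patient whom the documents do not report. One such patient at 200 mg Q12H is worth about 1.2 to 1.5 percentage points in fits linear in twice-daily or total daily dose, well inside limits that run from about 2% to 50%. The selected MTD is unchanged in every fit. These figures rest on no DLTs at the seven other levels and on the assumed cohort sizes.

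The choice of dose metric moves the estimate more than the population does (5.8-7.3% against 11.2-12.2% with n = 7), though it too leaves 200 mg Q12H as the MTD. The Parts B-G window is a contradiction between protocol and SAP with a possible effect on accrual review. The documents do not show that any event fell in those days.

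Nothing here supports a conclusion that the established MTD is wrong. It followed from the observed counts.

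**What to change.** - **SAP 6.2:** add a Part A DLT-evaluable set that excludes only patients discontinued from the study before 75% of planned Cycle 1 doses without a DLT. Patients who omitted doses but stayed on study remain in.
- **Appendix 2:** use that set for 14.2-1.1 and 14.2-1.2. Keep the at-least-one-dose set for DLT listings and summaries.
- **SAP 6.3.5.1:** state the dose metric and how the two schedules are handled. If the schedules are pooled, mg per administration should not be the default, because it misorders daily exposure as in step 6.
- **Windows:** reconcile the Parts B-G DLT-equivalent window between Protocol 6.2.2.1 and SAP 6.1.1 and 6.3.5.1, so that Days -3 to -1 are treated one way in the 33% review. Reconcile the end of the Part A DLT window between Protocol 6.2.2.1 and SAP 6.1.1. The choice of window is for the sponsor and investigators.
- **Editorial:** use one form of the 33% inequality throughout.

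The cost is SAP wording, one derived set and a matching protocol clarification. No new data are needed.

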#### **6.3.5.2. Adverse Events**

Pre-existing conditions are events that occur prior to the first dose of study drug. Pre-existing conditions are collected on the AE page and will be included in the AE listing.

Adverse events will be classified into 3 periods: On therapy (AE starts after the first dose), Follow-up (AE starts after the last dose) and more than 30 days (AE starts after 30 days of the last dose). The incidence of AEs will be summarized by cohort and period, taking into account CTCAE grade, relationship, seriousness, and cycle. Events will be summarized by CTCAE code (category and term) and, when necessary, MedDRA terms.

If the CTCAE category is not in the database, it will have to be programmed by assigning the category to the range of Lilly determined codes associated with the terms in each category.

MedDRA versions may be upgraded as frequently as twice in a year. Therefore, different MedDRA versions will be used in the database of this trial, based on when the AE information is received. However, the data will be summarized and listed in preferred terms (PTs) of the most current version of MedDRA at the time of reporting. Safety information collected with previous versions of MedDRA will be updated at the PT and system organ class (SOC) level to the most current version in the locked database. The version used in any report will be documented.

[Appendix 2](#) lists outputs to be generated. Adverse events, treatment-emergent adverse events (TEAEs), deaths and serious adverse events (SAEs) will be listed and summarised.

Summaries for patients on therapy by cohort will include:

- Listing of Patients who Discontinued due to Adverse Events or Death
- Listing of Deaths Reported
- Listing of Serious Adverse Events
- Listing of Pre-existing Conditions and Adverse Events
- Summary of Pre-existing Conditions – Preferred Term by Decreasing Frequency within System Organ Class
- Summary of Adverse Events – Preferred Term by Decreasing Frequency within System Organ Class (regardless of relatedness to study drug)
- Summary of Study Drug Related Adverse Events – Preferred Term by Decreasing Frequency within System Organ Class
- Summary of Maximum Laboratory Investigator Determined CTC Adverse Events Grade Post-baseline – Regardless of Study Drug Relatness
- Summary of Maximum Laboratory Investigator Determined CTC Adverse Events Grade Post-baseline – Possibly Drug Related
- Summary of Treatment Emergent Adverse Events by MedDRA System Organ Class and Preferred Term
- Summary of Treatment Emergent Adverse Events by Relation to Study Drug

